5.2 Primary Efficacy Analyses

5.2.1 Primary Analyses of Primary Efficacy Variable

For each of the BOTOX doses of 200 U and 100 U, the null hypothesis is that there is no difference between that dose group and the 50 U BOTOX dose group in mean change from baseline in daily average frequency of daytime urinary incontinence episodes at week 6. The alternative hypothesis is that there is a difference in mean change from baseline in daily average frequency of daytime urinary incontinence episodes between the higher BOTOX dose group under consideration and the 50 U dose group at week 6.

The hypotheses will be tested using an ANCOVA model with baseline value as covariate and treatment group, age (< 12 years or \geq 12 years), baseline daytime urinary incontinence episodes (a total of \leq 6 episodes or $>$ 6 episodes over the 2-day diary collection period), and use of anticholinergic therapy (no/yes) at baseline (on day of injection) as factors.

Furthermore, the last observation carried forward (LOCF) method of imputation will be used to impute missing week 6 assessments. The fitted model will be used to derive the adjusted mean treatment differences in the primary variable (least-squares [LS] mean difference) and

[figure not shown]
associated 95% CI, for the comparison of the 50 U BOTOX treatment group versus the 200 U and 100 U BOTOX treatment groups.

After fitting the ANCOVA model, to adjust for multiplicity, a hierarchical analysis testing strategy (Lubsen and Kirwan, 2002) will be applied. Initially the 200 U versus 50 U BOTOX mITT treatment group will be tested at a two sided significance level of 5%. If it is concluded that the 200 U BOTOX treatment group has a greater mean reduction in daily average frequency of daytime urinary incontinence episodes, the 100 U versus 50 U BOTOX treatment group will be tested. In other words, results of hypothesis testing for 100 U versus 50 U BOTOX will only be considered for statistical significance if the treatment difference for 200 U versus 50 U BOTOX is shown to be statistically significant.

Furthermore, the average daytime duration will be summarized for each visit.

Apart from the hierarchical testing, the analysis outlined above will also be repeated for the week 2, and 12 visit diary assessments. No imputation method will be applied in these analyses.

For each post-baseline visit, the primary efficacy variable will also be summarized for each treatment arm using mean, median, standard deviation, min, max and t-distribution based 95% confidence interval.

5.3 Secondary Efficacy Analyses

The following secondary efficacy variables that are based on patient diary data will be assessed.

- the percentage of patients that have a $\geq 50\%$, $\geq 75\%$, $\geq 90\%$, and 100% reduction from baseline in the number of normalized daytime urinary incontinence episodes
- change from baseline in average urine volume at first morning catheterization (mL)
- presence or absence of night time urinary incontinence

[figure not shown]
The following secondary urodynamics efficacy variables will be assessed at week 6 posttreatment

- change from baseline in maximum cystometric capacity (mL) (MCC)
- The proportion of patients with presence of involuntary detrusor contraction (IDC)
- if an IDC is present, change from baseline in maximum detrusor pressure during the first IDC ($P_{detMax1stIDC}$) (cm H₂O)
- change from baseline in maximum detrusor pressure (P_{detMax}) (cm H₂O) during the storage phase
- if leak occurs, change from baseline in detrusor leak point pressure (DLPP) (cm H₂O)

No imputation will be used for the missing values of secondary efficacy variables. A hierarchical analysis strategy to adjust for multiplicity will not be implemented.

5.3.1 Analysis of the Number of Patients that have Reduction from Baseline in Daytime Urinary Incontinence Episodes that Meet Certain Thresholds

The number of patients that have reduction from baseline in daily average frequency of normalized daytime urinary incontinence episodes [REDACTED]

5.3.2 Urine Volume at First Morning Catheterization (mL)

For urine volume at first morning catheterization (mL), the mean baseline, mean raw values and mean change from baseline at each visit and associated 95% CI for the mean change from baseline will be derived for each treatment group. For visits up to week 12 posttreatment, an ANCOVA model similar to the primary ANCOVA model will be fitted to the change from baseline value. The model will include the baseline value as covariate and treatment groups, age (< 12 years or ≥ 12 years), baseline daytime urinary incontinence episodes (a total of ≤ 6 episodes or > 6 episodes over the 2-day diary collection period), and anticholinergic therapy use (no/yes) at baseline as factors. The resulting adjusted treatment difference (LS mean difference) and associated 95% CI of the treatment difference in mean change from baseline will be derived for the comparison of the higher BOTOX dose groups versus the 50 U BOTOX group.

5.3.3 Presence or Absence of Night Time Urinary Incontinence

For the analysis of night time urinary incontinence, the numbers (percentage) of patients who experienced night time urinary incontinence on 0, 1, or 2 nights will be presented at study baseline and at each visit.

5.3.4 Analysis of Urodynamics Parameters

Urodynamics parameters are only assessed at screening (baseline) and at week 6 posttreatment. For urodynamic parameters only the central reviewer's assessment will be analyzed.

For the following urodynamics parameters:

1. maximum cystometric capacity (mL) (MCC),
2. maximum detrusor pressure ($P_{det_{Max}}$) during the storage phase (cm H₂O),
3. if IDC is present, maximum detrusor pressure ($P_{det_{Max1stIDC}}$) during the first IDC (cm H₂O), and
4. if leak occurs, detrusor leak point pressure (DLPP) (cm H₂O),

values at the two visits (baseline and week 6) and change from baseline values for week 6 posttreatment will be summarized. Furthermore, an ANCOVA model will be fitted and used to derive adjusted treatment means and treatment difference estimates for the comparison of the lower dose (50 U) with the higher BOTOX dose groups. The explanatory variables in the model will include the same explanatory variables listed for the primary efficacy variable analysis however, the covariate will be the baseline effect for each parameter under consideration.

[figure not shown]
For urodynamics parameter #3, change from baseline value can only be derived when maximum detrusor pressure ($P_{det_{Max1stIDC}}$) during the first IDC is present at both baseline and post-baseline visit (ie, an IDC occurs at both baseline and at week 6). Similarly, for urodynamics parameter #4, change from baseline value can only be derived if a leak occurs during the urodynamics procedure at both baseline and week 6 visit. In both cases (analysis of #3 and #4), if less than 25% of the mITT patients have change from baseline values, the ANCOVA model may not be fitted.

[figure not shown]
The number (percentage) of patients with presence of an IDC at baseline and at week 6 posttreatment will be summarized by treatment groups. Associated 95% confidence interval will also be generated. The difference at baseline and at week 6 posttreatment in the proportions of patients with presence or absence of an IDC between the treatment groups will be analyzed using the CMH methodology as described for the analysis of percentage patients meeting a threshold of reduction in daytime urinary incontinence episodes [REDACTED].

[REDACTED]

[REDACTED]

[REDACTED]

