### **4.2 Study Population Characteristics**

This study will include patients 5 to 17 years of age with urinary incontinence due to NDO who have not been adequately managed with anticholinergics.

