### 7.3.2 Secondary Efficacy Analyses

### **7.3.2.2 Efficacy Analyses for the Secondary Efficacy Variables**

[figure not shown]
The analysis of MCC, PdetMax, and average urine volume at first morning catheterization at week 6 after treatment will generally be analyzed as described for the primary efficacy endpoint in Section 7.3.1, except that the hierachal testing strategy will not be implemented. For the urodynamic variables, only the central reviewer's interpretation will be analyzed.

[figure not shown]
For analysis of MCC, data will also be presented as a proportion of the EBC, where EBC = (30 + [age in years × 30]) for volumes below the adult volume of 500 mL (age is at the time of the assessment).

The proportions of patients with presence/absence of an IDC at week 6 will be presented and analyzed using the CMH method (200 versus 50 U BOTOX and 100 versus 50 U BOTOX) controlling for age (< 12 years or ≥ 12 years), baseline daytime urinary incontinence episodes (a total of ≤ 6 episodes or > 6 episodes over the 2-day diary collection period), and concurrent anticholinergic therapy (use or non-use).

For the analysis of night time urinary incontinence, the numbers and proportions of patients who experienced night time urinary incontinence on 0, 1, or 2 nights will be presented.

Analysis of time to patient request for retreatment and time to patient qualification for retreatment will be performed as described in Section 7.3.3.4 Duration of Effect.

AUC = area under the curve

[REDACTED]  
[REDACTED]  
[REDACTED]  
[REDACTED].

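### Adding age in years to the ANCOVAs for cystometric capacity and first-morning urine volume, which use age only as <12 / ≥12, may gain precision at almost no cost; the planned models are not in error

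*SAP*

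**What the plan says.** The primary model in SAP 5.2.1 has the baseline value as covariate and treatment group, age in two levels, baseline episodes in two levels and anticholinergic use as factors. SAP 5.3.4 applies it to the urodynamic variables, MCC among them: "The explanatory variables in the model will include the same explanatory variables listed for the primary efficacy variable analysis". The one substitution is that "the covariate will be the baseline effect for each parameter under consideration".

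SAP 5.3.2 writes the model for first-morning volume out in full, for visits up to week 12: "The model will include the baseline value as covariate and treatment groups, age (< 12 years or ≥ 12 years", followed by the same two remaining factors.

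Protocol 7.3.2.2 adds a size-scaled view for one of the two outcomes: "For analysis of MCC, data will also be presented as a proportion of the EBC". The denominator of that proportion is defined by a formula in age: "where EBC = (30 + [age in years × 30]) for volumes below the adult volume of 500 mL". Protocol 6.1.2 takes age at the time of the assessment for this calculation. No test is named for the proportion, and no such scaling is stated for first-morning volume. The readable SAP text does not mention EBC, although part of the text after 5.3.4 is redacted.

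**The concern.** The covariates were chosen for a count of incontinence episodes and then reused for two volumes. Bladder volume grows with the child, and the trial enrols ages 5 to 17. If the change in mL also grows with age, a two-level factor leaves part of that variation in the error term, and the 200 U and 100 U versus 50 U intervals are wider than they need be, with about 30 patients per group.

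The dose-cap rule raises a second question. Protocol 7.1 and SAP 2.1 move patients who received less than their randomized dose because of the 6 U/kg limit into the nearest dose group. The lightest children, who tend to be the youngest, therefore leave the analysed 200 U group, and a <12 / ≥12 factor cannot see an age difference that arises inside the younger stratum.

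**Working it through.** **Plan figures.** No SD, effect size or precision target is given for MCC or morning volume. The only precision table (Protocol 7.7) is for the primary endpoint. Its first line reproduces: 1.96 × 2.0 × √(2/30) = 1.012. From it I take 30 patients per group.

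**EBC by age**, min(30 + 30 × age, 500):
- age 5: 30 + 150 = 180 mL
- age 11: 30 + 330 = 360 mL, double the value at 5
- age 12: 390 mL
- age 15: 480 mL
- ages 16 and 17: capped at 500 mL, so the older stratum rises by 500/390 − 1 = 28%

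**How much the two-level factor already removes.** Assume whole-year ages spread evenly over 5–17 (7 ages under 12, 6 at or above). Within-stratum SDs of EBC are 60.0 and 41.1 mL, so the within variance is (7 × 3600 + 6 × 1689)/13 = 2718. Stratum means are 270 and 456.7 mL, so the between variance is (7 × 6/13²) × 186.7² ≈ 8660. The within share is 2718/(2718 + 8660) = 24%; the factor takes about 76% before baseline mL is used.

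**Cost of one more term.** With 90 patients the planned model has 7 coefficients and 83 residual degrees of freedom. An eighth leaves 82. A useless covariate inflates the SE by √(83/82) = 1.006, or 0.6%.

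**Possible gain.** Net SE ratio = √[(1 − partial R²) × 83/82], where partial R² is that of continuous age given baseline mL and the age factor. A 12% reduction needs partial R² = 1 − 0.88² × 82/83 = 0.235.

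Partial R² must be assumed. Trial-size simulation of MCC, 30 per randomized group, 60% under 12, baseline mean 50% of EBC with CV 0.4 unless stated, correlation 0.5, no treatment effect:

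| Assumed week 6 MCC (mean, SD, as % of EBC) | SE planned (mL) | SE with EBC (mL) | Ratio |
|---|---|---|---|
| 60, 15 | 13.6 | 12.4 | 0.91 |
| 70, 20 | 17.1 | 16.2 | 0.95 |
| 70, 30 | 24.9 | 24.6 | 0.99 |
| 90, 15 (baseline 60, CV 0.5) | 15.9 | 12.4 | 0.78 |

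The simulated models omit the episode and anticholinergic factors. A rerun with both included as unrelated factors gave the same average model-based SE ratios. The last row pairs a 30-point mean gain with a small SD and is an extreme. In large-sample calculations over a wider grid (baseline 40–60% of EBC, correlation 0.3–0.7), partial R² ran from 0.00 to 0.46. If the mL gain does not depend on age, partial R² is zero and only the 0.6% cost remains. A separate set of trial-size runs under assumed MCC distributions, net of the degree of freedom, gave about 0 to 12%.

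**Regrouping.** The cut-offs in SAP Table 1 are 75 U and 150 U. By direct arithmetic 6 × 25 kg = 150 U and 6 × 12.5 kg = 75 U. A child randomized to 200 U and weighing under 25 kg is analysed as 100 U, or as 50 U below 12.5 kg, whereas a child of 20 kg randomized to 50 U stays there. (The preparation tables of Protocol 12.1 are not in the public text.) With an assumed weight-for-age curve, no true effect and the four scenarios above, the planned model gave a mean 200 U versus 50 U difference of 4.9, 6.3, 4.4 and 9.5 mL against SEs of 14.7 to 28.0 mL. With EBC added it was −0.3, 0.6, 0.2 and −0.3 mL. Across the other weight curves and MCC distributions tried, the shift was about 1 to 11 mL in size, usually favouring 200 U, and about 1 mL or less after adding age or EBC.

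**The case against.** The strongest reply is that nothing is wrong. ANCOVA on baseline and the randomization strata is conventional and valid, Protocol 7.3.2.2 says these outcomes will generally follow the primary analysis, and the SAP does so. They are secondary endpoints outside the hierarchy. The two-level factor and baseline mL already carry much of the size information, and the MCC/EBC proportion applies exact age directly, if only descriptively. Redacted SAP text may contain more. All of this stands, and it is why the point is an improvement and not a fault.

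A reader might go further and infer from the doubling of EBC that precision is certainly lost, or that two age levels cannot capture growth. The documents do not support that. The formula describes expected capacity in children generally; it says nothing about change after treatment in these patients, and the gain can be nil. Nor can the MCC range be lent to first-morning volume: the documents apply EBC to MCC and to cystometric filling, never to that outcome.

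The appeal to randomization is weaker than usual, because the analysed groups are not the randomized ones. A reader might conclude that the dose comparison is therefore materially biased. That too goes beyond the evidence: the shift rests on an assumed weight curve and was well below one standard error in every scenario tabulated above.

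**Conclusion.** A worthwhile, nearly free refinement of two secondary analyses. The documents establish three things: both outcomes are modelled as change in mL with a two-level age term, the protocol's own formula doubles from 180 to 360 mL inside the younger level, and exact age is already in hand. They do not establish the size of the benefit. For MCC, a net fall in the standard error of about 0 to 12% is a reasonable working range at 30 per group; the most favourable assumptions tabulated reach 22%, and the least favourable give a loss of 0.6%. For first-morning volume no figure can be given. The possible age imbalance from regrouping is a supporting reason for the same change, worth a few mL under assumed weights. Neither the primary endpoint nor type I error control in the primary hierarchy is touched.

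**What to change.** Before database lock, add age in years (or EBC) as a continuous covariate to the MCC model in SAP 5.3.4 and to the first-morning-volume model in SAP 5.3.2 at every visit where it is fitted (weeks 2, 6 and 12). Keep the <12 / ≥12 factor because it was used to stratify. Fix the covariate at its baseline value, since EBC computed at the assessment can change with a birthday. Choose age or EBC in advance, not after seeing results.

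Record the addition as a change from Protocol 7.3.2.2; SAP Section 12 now states that there are no deviations. The cost is one degree of freedom in each of four models, under 1% of the standard error, and no new data.

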2.3 Data Conventions

The following data conventions will be applied to all analyses.

- A patient's weight adjusted dose will be derived using the randomization information and the patient's actual weight provided in IVRS/IWRS at baseline.
- Unless stated otherwise, all statistical tests will be at a 2-sided significance level of 0.05. P-values ≤ 0.050 will be considered statistically significant.
- Since the qualification for retreatment may occur anytime from week 12 onwards, no statistical tests for pairwise comparison of treatment groups will be performed for any visit beyond week 12.
- The type III sums of squares will be used for all analysis of covariance models (ANCOVA).
- The variance for Kaplan-Meier estimates will be calculated using Greenwood's formula.
- Descriptive statistics for continuous variables include the sample size (N), mean, SD, median, minimum (min), first quartile (Q1), third quartile (Q3), and maximum (max).

- Summary statistics for categorical variables include the sample size (N), frequency count and percent.
- The Medical Dictionary for Regulatory Activities (MedDRA) dictionary will be used to code all adverse events (AEs) and medical history.
- World Health Organization Drug Dictionary Enhanced (WHO DDE) preferred name and MedDRA will be used to code all medications.
- Study duration from day 1 (injection date) will be calculated as:

Study day in study = visit date – day 1 date + 1.

- For vital signs and laboratory summary tables, baseline is defined to be the last assessment prior to BOTOX injection.
- For by visit, vital signs and laboratory summary tables, there will also be a summary of the last post-baseline assessment.
- The algorithm presented in [Table 3](#), together with the rules below will be used to impute incomplete or missing dates for adverse events and medications as follows:
 - (a) AE start dates will be imputed as the minimum of the following:
 - initial imputed date, where target date = study drug injection date
 - complete end date
 - (b) Medication start dates will be imputed as the minimum of the following:
 - initial imputed date, where target date = study drug injection date – 1
 - complete end date
 - (c) AE and Medication end dates will be imputed as the minimum of the following:
 - initial imputed date, where target date = study exit date + 30
 - death date

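### SAP 5.3.4: the dose differences planned for first-IDC pressure and DLPP are conditional on a week 6 event that dose can change, and should be labelled as such

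*SAP*

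**What the plan says.** SAP 5.3.4 lists four continuous urodynamic parameters, measured at screening and week 6. For all four, "an ANCOVA model will be fitted and used to derive adjusted treatment means and treatment difference estimates" between 50 U and the higher doses.

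Two of them exist only if something happens during the test:

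- **Parameter 3, PdetMax1stIDC.** A change value needs the pressure "during the first IDC is present at both baseline and post-baseline visit (ie, an IDC occurs at both baseline and at week 6").
- **Parameter 4, DLPP.** Here, "change from baseline value can only be derived if a leak occurs during the urodynamics procedure at both baseline and week 6 visit".

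SAP 5.3 rules out imputation for secondary variables. The only limit placed on the two models is that "if less than 25% of the mITT patients have change from baseline values, the ANCOVA model may not be fitted".

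The same section also plans a Cochran-Mantel-Haenszel (CMH) analysis of the difference "in the proportions of patients with presence or absence of an IDC between the treatment groups", at baseline and at week 6.

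**The concern.** An ANCOVA on randomised groups estimates a dose effect because the groups were comparable at the start. Restricting it by a baseline feature keeps that property. Restricting it by something that happens after treatment need not, because the patients left in each arm may have been selected differently.

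Here the week 6 half of the condition is such an event. If a higher dose abolishes more contractions, the 200 U patients who still have one may differ from the 50 U patients who still have one, apart from any effect of dose on pressure. The adjusted differences could then be read as randomised dose effects on pressure when they are not. What is at stake is the interpretation of two secondary variables, one of which (first-IDC pressure) was a secondary urodynamic endpoint in the adult pivotal studies described in Protocol 1.

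**Working it through.** **The plan's own figure.** The only precision figure is in Protocol 7.7 and concerns the primary variable. The half-width 1.960 × SD × √(2/30) gives 1.012, 1.265, 1.518, 1.771 and 2.024 for SD 2.0 to 4.0, as printed. There is no such figure for urodynamics, and this point contests none.

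**Is the condition a post-randomisation outcome?** Three places answer this.

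- Protocol 7.2.2 and SAP 5.3 list IDC presence at week 6 as a secondary efficacy variable.
- SAP 5.3.4 compares it between doses.
- Protocol 1 names inhibition of detrusor contraction as a target of the drug.

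So dose can change who contributes a change value. The documents do not show that it does, or by how much.

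**What the 25% rule does.** Taking all 102 randomised patients as mITT, 0.25 × 102 = 25.5, so 26 patients are enough. They are pooled over three arms: 26/3 is about 9 per arm, and no minimum applies to any one arm. The rule is also optional. It concerns the amount of data and says nothing about who is selected.

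**How far could the contrast move?** No event rates or pressure SDs are given, so every input here is an assumption.

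- Let p50 and p200 be the proportions with the event at week 6 among patients who had it at baseline.
- Assume that 200 U never restores an event that 50 U would have removed.
- Assume that the residual change in 50 U patients with the event is normal with SD s.

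Then a fraction q = 1 − p200/p50 of those 50 U patients would have lost the event on 200 U. In the worst case they all lie at one end of the distribution. The 50 U mean then differs from that of patients who would have the event on either dose by s × φ(z_q)/(1 − q), in either direction.

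| p50 / p200 (assumed) | q | Worst-case shift | At s = 15 to 25 cm H2O (assumed) |
|---|---|---|---|
| 75% / 75% | 0 | 0 | 0 |
| 90% / 80% | 0.111 | ±0.213 s | 3.2 to 5.3 |
| 75% / 60% | 0.200 | ±0.350 s | 5.2 to 8.7 |
| 75% / 50% | 0.333 | ±0.545 s | 8.2 to 13.6 |

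The last column uses unrounded multipliers.

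**A less extreme model.** A simulated baseline-adjusted ANCOVA was restricted to patients with the event at week 6. It assumed a baseline to week 6 pressure correlation of 0.5, a correlation of 0 to 0.7 between week 6 event propensity and pressure, and no true dose effect on pressure. The 200 U minus 50 U difference was:

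- about 0 at 80% versus 80%;
- 0 to +0.17 SD at 80% versus 60%;
- 0 to +0.35 SD at 80% versus 40%.

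The bound formula gives 0.42 s and 0.80 s for the last two pairs. With s = √(1 − 0.5²) = 0.866 SD, these are 0.37 and 0.69 SD, so the largest simulated shifts are about half the bounds. The positive sign follows from the assumed positive correlation.

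**What is free of the condition.** Protocol 12.3.5 defines PdetMax as the highest storage-phase pressure from any source, so it needs no IDC. IDC presence is analysed whichever way the week 6 test turns out.

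**The case against.** The strongest reply is that the condition is inherent and disclosed. A first-IDC pressure does not exist without an IDC. Both documents attach the qualifier to these variables, and SAP 5.3.4 spells out the both-visits consequence. That stands as a defence of the derivation. It does not cover the contrast, because the readable text places no limit on interpreting the adjusted differences. Table shells are not in the documents, so it cannot be said that the outputs will lack a label.

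Much context is already planned. "The number (percentage) of patients with presence of an IDC at baseline and at week 6 posttreatment will be summarized by treatment groups", with confidence intervals. SAP 2.3 adds that "Descriptive statistics for continuous variables include the sample size (N), mean, SD, median" and further statistics, so N at each visit already counts DLPP values by arm. What the readable text lacks is the reason why change values are missing, and parts of the section are redacted.

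Deleting the two ANCOVAs would also overcorrect. By-arm descriptive changes carry the same selection and lose the baseline adjustment. That stands, and the fix keeps the models.

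A reader might infer three further things that the documents do not support.

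- **That the SAP redefines DLPP to include leaks during an IDC.** Its sentence states a necessary condition in the protocol's own shorthand. The definition in Protocol 12.3.5 still applies.
- **That these ANCOVAs depart from the protocol.** The visible text of Protocol 7.3.2.2 says that MCC, PdetMax "and average urine volume at first morning catheterization at week 6 after treatment will generally be analyzed as described for the primary efficacy endpoint" and does not name the other two. But text is missing around that sentence. The Protocol Summary, 7.2.2 and 7.3 all support an ANCOVA for these variables, so the SAP 12 statement of no deviations is not contradicted.
- **That the bias is known to hide or inflate a benefit of the higher dose.** Any direction comes from assumed correlations.

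**Conclusion.** The point holds as a minor matter of analysis and interpretation. The planned differences between 50 U and the higher doses in change in PdetMax1stIDC and DLPP are conditional on an event at week 6 that dose can change. Randomisation does not protect them, and the 25% rule does not address this.

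Neither the size nor the direction of any bias can be taken from the documents. The figures above are worst-case bounds, or simulations, on assumed persistence rates, SDs and correlations. They should not be read as expected bias. Both variables are secondary, and the primary conclusion is untouched.

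**What to change.** In SAP 5.3.4:

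1. State that the ANCOVA results for parameters 3 and 4 are descriptive, conditional on the event at both visits, and not to be read as randomised dose effects. The models may stay for baseline adjustment.
2. Beside them, show by arm the number of mITT patients without a change value and the reason: no event at the baseline test, no event at week 6, or no week 6 test. The first is possible for IDC because Protocol 6.3.7 lets a historical evaluation satisfy eligibility.
3. Base between-dose conclusions on the PdetMax ANCOVA and the CMH analysis of IDC presence, both already planned.

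The cost is a few sentences and one small table, with no new data. The downside is that no inferential claim can be made for two secondary variables, including first-IDC pressure.
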